15.0 Other Approvals and Registrations

15.1 * Do any study activities take place on patient care units:

Yes No

If **Yes**, attach a letter of support for the study from the involved patient care manager(s).

15.2 * Does your protocol involve any radiation exposure to patients/subjects? The UCSF Radiation Safety Committee requires review of your protocol if it includes administration of radiation as part of standard of care OR research exposures:

Yes No

15.3 * This study may generate genetic data that may be broadly shared (e.g. submitted to NIH for Genome-Wide Association Studies (GWAS) in dbGaP, TCGA, etc):

Yes No

15.4 * This study involves administration of vaccines produced using recombinant DNA technologies to human subjects:

Yes No

15.5 * This study involves human gene transfer (NOTE: Requires NIH Recombinant DNA Advisory

Committee (RAC) review prior to CHR approval):

Yes No

15.6 This study involves other regulated materials and requires approval and/or authorization from the following regulatory committees:

Institutional Biological Safety Committee (IBC)

Specify BUA #:

Institutional Animal Care and Use Committee (IACUC)

Specify IACUC #:

Radiation Safety Committee

Specify RUA #:

Radioactive Drug Research Committee (RDRC)

Specify RDRC #:

Controlled Substances

16.0 Procedures**16.1 * Procedures/Methods (Help Text updated 9/13) For clinical research list all study procedures, test and treatments required for this study, including when and how often they will be performed. If there are no clinical procedures, describe the Methods:**

Schedule of Evaluations. The table below provides an overview of study procedures and the schedule of evaluations. Briefly, screening will be performed by telephone and will include assessment of demographics and eligibility criteria. The consent visit will be performed in person with the participant and legally authorized representative (LAR) together; detailed consent procedures are provided in the Informed Consent section. After consent has been obtained, global cognitive function will be assessed in participants. The LAR may serve as the study caregiver or may designate someone else (e.g., other family member, paid caregiver) to play this role. The baseline, 4-month and 8-month visits will be performed with the participant and caregiver separately and will include measurement of participant and caregiver outcomes and potential confounders and mediators. Adverse events and co-interventions (e.g., medication changes) will be assessed during monthly caregiver check-ins during the intervention period. Each visit is described in more detail below. All of these research-related activities will be performed by our research team. Staff at the study sites will NOT be engaged in research and will be responsible for referring potential participants to our research team for screening; escorting study participants to and from the exercise intervention space; assisting study participants who need to use the toilet; and providing space for our exercise instructors to deliver the intervention.

Overview of Study Procedures and Schedule of Evaluations

	Screening	Consent	Baseline	4 Months	8 Months	Monthly CG Check-ins
Eligibility	X					
Demographics/ medical history	X					
Capacity to Consent		X				
Informed Consent		X				
Global cognitive function		X				

Outcomes			X	X	X	
Confounders/ mediators	nnn	nnn	X	X	X	
Adverse events						X
Co-Interventions						X

Screening (telephone, LAR/CG). Legally authorized representatives (LARs) of potential participants who have expressed interest in being contacted will be screened for eligibility over the telephone. Basic demographic and medical history information also will be collected after obtaining verbal consent. This information will be collected during screening in order to compare characteristics of those who choose to participate or not to assess for potential selection biases. Those who are eligible and interested will then be scheduled for an in-person consent visit. LARs may also serve as the study caregiver or may designate someone else (e.g., other family member, paid caregiver) to play this role. If an alternate study caregiver is designated, they will be screened and consented separately or consented with the LAR and potential participant if possible.

Consent Visit (in person, participant and LAR together). Similar to our pilot study, informed consent will be obtained with the participant and LAR together at a location of their choosing (e.g., home, SFVA, adult day center). Detailed consent procedures are provided in the Informed Consent section. In addition, the Montreal Cognitive Assessment (MoCA) will be administered to participants to measure global cognitive function. The MOCA is often used in clinical settings and will be used as a descriptive measure for clinical audiences to characterize dementia severity and also in exploratory analyses to determine whether baseline cognitive status acts as a confounder or effect modifier of the effects of PLIÉ. If an alternate CG is designated, they may be consented with the primary participant or at another time and place.

Baseline Assessment (with participants and caregivers separately). The baseline assessment may be performed immediately after the consent visit or scheduled for a later date. Participants and caregivers will provide data separately so that their answers do not influence each other. Participants will be directly assessed by research staff while caregivers will be provided with self-administered forms when feasible or may complete the assessment in person, by phone or mail-in.

Baseline Assessments in Participants

- Cognitive function (Alzheimer’s Disease Assessment Scale – Cognitive Subscale, ADAS-cog). Cognitive function will be measured using the Alzheimer’s Disease Assessment Scale – cognitive subscale (ADAS-cog). The ADAS-cog is one of the most commonly used outcome measures in dementia drug treatment trials and is one of the measures considered by the Food and Drug Administration for approval of dementia medications. It includes direct assessment of learning (10-word list), naming (objects), following commands, constructional praxis (figure copying), ideational praxis (mailing a letter), orientation (person, time, place), recognition memory and remembering test instructions and is scored on an 80-point scale with higher scores reflecting worse cognitive function. Prior studies have found the ADAS-cog to be valid and reliable with Cronbach’s alpha greater than 0.8 and test-retest reliability above 0.9.

- Physical performance (Short Physical Performance Battery (SPPB)). The SPPB was developed by the National Institute on Aging to provide an objective tool for measuring physical performance in older adults. **Lower body strength** is assessed based on time to complete 5 chair stands without using arms. **Balance** is assessed based on the ability to hold different stands for 10 seconds, including the side-by-side, semi-tandem and full tandem stands. **Mobility** is assessed based on usual walking speed over a 3-meter walking course. The **total SPPB score** is the sum of the 3 component scores and may range from 0 to 12. Prior studies have found that the SPPB is valid and reliable and associated with important outcomes including disability and mortality. A recent systematic review concluded that the SPPB was one of the best tools available to measure physical performance in older adults based on reliability, validity and responsiveness.

- Quality of life (Quality of Life Scale in Alzheimer’s Disease, QOL-AD). The Quality of Life Scale in Alzheimer’s Disease (QOL-AD) is a standard quality of life measure that asks parallel questions of affected individuals and caregivers and was used in our pilot study. Current quality of life is rated as poor (1 point), fair (2 points), good (3 points) or excellent (4 points) in 13 areas: physical health, energy, mood, living situation, memory, family, marriage, friends, self as a whole, ability to do chores around the house, ability to do things for fun, money, and life as a whole. Scores may range from 13 to 52 with higher scores reflecting better quality of life. Prior studies have found that the QOL-AD is a valid and reliable measure, with Cronbach’s alpha of 0.84 for patient reports and 0.86 for caregiver reports and interrater reliability based on Cohen’s kappa values >0.70.

- Falls Efficacy Scale. A standard measure of falls efficacy that can be administered to people with cognitive impairment or caregivers and asks about concern about the possibility of falling doing 10 daily tasks (e.g., taking a bath or shower) on a 4-point likert scale (not at all, somewhat, fairly or very concerned).

- Near-Infrared Spectroscopy (NIRS). A non-invasive optical method that measures blood oxygenation changes in the brain tissue. The NIRS method will be used in combination with the Verbal-Fluency Task, a cognitive task that is known to activate frontal brain areas. A few studies have used the Verbal Fluency

Task with NIRS (Herrmann, Ehlis, & Fallgatter, 2003), including in individuals with Alzheimer's disease (Fallgatter, Sitzmann, Heidrich, Mueller, & Strik, 1997).

Baseline Assessments in Caregivers

- Caregiver burden (Caregiver Burden Inventory, CBI). The Caregiver Burden Inventory (CBI) is a standard measure that includes 24 items and 5 domains. Caregivers are asked to rate how often each statement describes their feelings (never, rarely, sometimes, quite frequently, nearly always). The total score may range from 0 to 96 with higher scores reflecting greater feelings of burden. The CBI has good internal consistency (Cronbach's alpha, 0.73-0.86), and it was sensitive to change in our pilot study.
- Participant function (Disability Assessment for Dementia, DAD). The impact of the intervention on functional independence will be assessed with the Disability Assessment for Dementia (DAD), which is a standard measure that asks caregivers to rate the participant's disability with 17 basic and 23 instrumental activities of daily living over the past 2 weeks. The DAD has high established validity and high test-retest reliability (ICC, 0.96), inter-rater reliability (ICC, 0.95) and internal consistency (Chronbach's alpha, 0.96).
- Participant dementia-related behaviors (Neuropsychiatric Inventory (NPI). The NPI assesses the frequency, severity and level of distress caused by 12 common dementia-related behaviors (delusions, hallucinations, agitation/aggression, depression/dysphoria, anxiety, elation/euphoria, apathy/indifference, disinhibition, irritability/lability, aberrant motor behavior, sleep and appetite/eating). The NPI has good test-retest reliability (0.79-0.86) and good internal consistency (Cronbach's alpha, 0.87-0.88).
- Participant quality of life (QOL-AD). As described above, the QOL-AD is a standard quality of life measure that asks parallel questions of affected individuals and caregivers and was used in our pilot study.
- Participant urinary incontinence. Urinary incontinence in participants will be assessed with questions about the frequency, amount and distress caused by accidental urine leakage.
- Participant Falls Efficacy Scale. A standard measure of falls efficacy that can be administered to people with cognitive impairment or caregivers and asks about concern about the possibility of falling doing 10 daily tasks (e.g., taking a bath or shower) on a 4-point likert scale (not at all, somewhat, fairly or very concerned).
- Positive Aspects of Caregiving Scale. A standard measure that asks caregivers to rate their agreement /disagreement with 11 statements about positive aspects of caregiving on a 5-point likert scale (disagree a lot ... agree a lot).
- Geriatric Depression Scale - short form. Depressive symptoms in caregivers will be measured based on self-report with the GDS-short form, a 15-item yes/not scale that is valid in people with and without dementia.

Randomization. Study participants will be enrolled in one study site at a time in blocks of 20, and the randomization sequence will be generated in advance in blocks of 20 (10 Group 1, 10 Group 2) using a random number generator on a computer. The sequence will be stored in a secure location accessible only to intervention staff, and research staff who enroll study participants and collect outcome data will be unaware of the randomization sequence.

Blinding. Because we are using a waitlist design with usual care as the control condition, it will not be possible to blind study participants or their caregivers. However, research staff who collect outcome data will be blinded to group assignment. Every effort will be made to ensure that blinding is maintained including: 1) having interviewers remind study caregivers not to discuss any aspect of the study or ask any questions related to the study prior to scheduling or performing assessments; 2) excluding interviewers from staff meetings that discuss details of the intervention; and 3) maintaining the group assignment list separately from other study documentation. Interviewers also will be asked to guess which group participants were in to assess the adequacy of the blinding procedures.

Intervention. The PLIÉ program has been rigorously developed and pilot-tested by our team over the past four years. It capitalizes on recent discoveries in neuroscience and experimental psychology, which have found that, although explicit memory (the ability to consciously learn and remember new information) is impaired in people with dementia, implicit memory (unconscious learning that typically occurs through repeated exposure) is relatively preserved, particularly procedural memory (unconscious learning of procedures). PLIÉ therefore focuses on training procedural memory for the ability to perform the movements that are most needed for daily function (e.g., transitioning safely from sitting to standing) while also increasing mindful body awareness and encouraging social connection. It combines elements from a wide range of Eastern and Western exercise modalities, including occupational therapy, physical therapy, yoga, tai chi, Feldenkrais, Rosen Method, dance movement therapy and mindfulness meditation. The **PLIÉ Core Exercise Sequence** is repeated at every class and includes: Greetings (5 minutes); Body awareness warm-up (5 minutes); Seated exercises (15 minutes); Sit-to-stand and standing exercises (15 minutes); and Closing & appreciations (5 minutes). In addition, the program is guided by the **PLIÉ Guiding Principles** (see below) for relating to class members, teaching exercise movements and utilizing goals and preferences. The PLIÉ program will be offered at each center for 1-hour sessions at least two days /week. Exercise instructors will prepare the exercise space and clean up after class as needed. Based on our prior experience, class size will be restricted to a maximum of 5 participants per instructor to ensure safety. In addition, participants will be offered a monthly home visit to help them incorporate movements

from the classes into their daily lives. Caregivers may participate in home visits, and support materials (e.g., instructional booklets, iPad minis with access to instructional videos on the PLIE website) may be provided. iPad minis will not be used to access the UCSF or VA networks.

PLIÉ Guiding Principles	Rationale	Exercise Approaches Integrated
1. Repetition with variation	The same basic sequence of events is repeated in each class, providing a structure that becomes familiar over time and is designed to promote procedural learning. Specific movements are varied to maintain engagement based on moment-to-moment participant responses and to include variations introduced by participants.	Physical therapy, occupational therapy, yoga, tai chi, dance movement therapy
2. Progressive, functional movements	Specific movement sequences are selected to be related to important daily functional activities such as standing safely from a seated position. Simpler movements build slowly toward more complexity.	Physical therapy, occupational therapy, Feldenkrais, Rosen
3. Slow pace and step-by-step instructions.	Movements are performed slowly to enable participants to fully process instructions. Step-by-step instruction and modeling are utilized to minimize the cognitive demands and promote procedural learning.	Occupational therapy, yoga, tai chi, Feldenkrais, Rosen, dance movement therapy
4. Participant-centered goal orientation.	A goals assessment is performed before beginning the program. Participants are motivated by relating movements to personal interests and goals.	Physical therapy, occupational therapy
5. Body awareness, mindfulness, and breathing	Periods of rest are included between movements. Participants are encouraged to breathe deeply; notice how their bodies feel aided by sensory stimulation such as tapping, touching and naming body parts; and share their observations with the group.	Yoga, tai chi, Feldenkrais, Rosen
6. Social interaction	Participants sit in a circle, and many movements involve reaching across the circle to touch hands or elbows, or standing in a circle holding hands and moving together to facilitate social connection.	Dance movement therapy, occupational therapy, Rosen
7. Positive emotions	The program promotes positive emotions by creating a warm, loving, non-judgmental, non-coercive environment in which participants are encouraged to move in ways that feel good to them. Brief musical selections are used to enhance positive emotions.	Occupational therapy, yoga, tai chi, Feldenkrais, Rosen method, dance movement therapy

Goals Assessment. Prior to beginning the PLIÉ program, exercise instructors will meet individually with study participants and caregivers to discuss their personal goals and interests. Goals may range from concrete objectives (reaching down to tie shoes) to more general objectives (remembering appointments). Prior studies have found that rehabilitation tends to have better outcomes when patients are involved with setting their own goals. Exercise instructors will also ask about hobbies and interests of study participants as well as potential barriers and facilitators to engaging in a group exercise program. Information gathered will be used in the class setting to help tailor exercises to address individual goals and interests and to

imbue exercises with greater meaning (e.g., this exercise may help you reach down to tie your shoes; being more aware of your body and the things around you may help you remember upcoming appointments).

Usual Care (UC) Control. Those participants attending the adult day program will participate in usual activities at the center, while those from the community will continue to engage in usual activities at home. All adult day programs include some type of group physical activity (usually seated) or individualized physical therapy. Whenever feasible, we will strive to offer PLIE classes at the same time as usual exercises at the center. We will document usual care activities by collecting monthly activity schedules from study sites and by asking caregivers about usual activities over the past month during check-ins to assess for potential co-interventions or contamination. This will enable us to perform exploratory analyses to assess the effects of different usual care activities on study outcomes.

Follow-Up Assessments (participants and caregivers separately). Follow-up assessments will be performed at 4 months and 8 months for all study participants. Procedures and measures will be identical to those at baseline.

Adherence, Adverse Events and Co-Interventions. Adherence will be monitored using class attendance logs. Adverse events will be assessed by calling caregivers on a monthly basis using a standardized questionnaire. Caregivers will be asked to report changes to the participant's health status since the last contact, including any emergency room visits, hospitalizations, or injuries. For any symptoms or events reported, caregivers will be asked if they occurred during or shortly after participating in PLIE or usual activities. Events that are serious and unexpected will be reported to an independent Data Monitoring Committee (DMC) and the IRB within 5 working days. The DMC also will review the adverse event log on a biennial basis. Based on consultations with the SFVA Research Office, adverse events that are possibly, probably or definitely study-related that occur in SFVA patients will be entered as notes into the medical record. Co-interventions also will be assessed during monthly caregiver check-ins using a standardized questionnaire that asks about any changes since last contact that might affect study outcomes including changes in medications, caregivers, medical conditions, usual activities or other factors.

Video-recording. Some of the exercise classes or assessments will be video-recorded for quality control, research or educational purposes. Everyone must consent to the video-recording for quality control and training purposes. The participants will have the option to allow for (1) private viewing only – viewing limited to the research team, auditors, and monitoring committee, or (2) private and public viewing – viewing available to the public as videos will be included in the training manual, shown at research or educational meetings, and/or posted on the study website.

Participant options for video recording will be tracked together with the main consent; i.e., that tracking will be included in the current study database. More specifically, the database includes a Consent section, under which the main consent, video recording options, and future contact consent options will be entered. This will ensure that the research team are kept informed of participant choices for video recording. Participants may be contacted after study ends regarding information about the optional participation in ongoing community classes, Participants will be sent birthday cards, and--in case of death or hospitalization--sympathy cards.

PIs are permitted to sending annual research progress reports to funding agencies and research colleagues.

Other contact with study participants. To maintain good relationships with study participants, we may send birthday cards, get well cards and sympathy cards using IRB-approved templates. In addition, we may send periodic research progress updates using IRB-approved letters.

Implementation activities. We have received additional support from the Department of Veterans Affairs through the VA Innovators program to begin implementing PLIE as a new clinical program within VHA. To facilitate this process, we will be interviewing key VA stakeholders, patients, caregivers and clinicians regarding optimal implementation strategies; analyzing interviews to identify key themes; creating a 3-minute video 'pitch'; and drafting an implementation plan. In addition, we may offer PLIE classes at the Community Living Center, adult day programs that contract with VHA and through the YMCAs. This is considered a quality improvement project. However, some prior PLIE participants who are Veterans may be involved.

Additional measures to assess impact of North Bay fires: For caregiver participants at the Primrose site only, the Perceived Stress Scale will be administered at the mid-point and final assessments to measure the impact of the North Bay fires on general stress levels. In addition, an open-ended questionnaire will ask about the perceived impact of the fires on key study outcomes. A cover letter will inform caregivers that two new questionnaires have been added and will remind them that all study procedures are optional.

If you have a procedure table, attach it to the submission with your other study documents.

16.2 Interviews, questionnaires, and/or surveys will be administered or focus groups will be conducted:

Yes No

List any standard instruments used for this study:

Alzheimer's Disease Assessment Scale – Cognitive Subscale (ADAS-cog)
Short Physical Performance Battery (SPPB)
Quality of Life Scale in Alzheimer's Disease (QOL-AD)
Near-Infrared Spectroscopy (NIRS)
Caregiver Burden Inventory (CBI)
Disability Assessment for Dementia (DAD)
Neuropsychiatric Inventory (NPI)
Falls Efficacy Scale (FES)
Positive Aspects of Caregiving (PAC)
Geriatric Depression Scale - Short Form (GDS)
Perceived Stress Scale (Primrose caregiver participants only, Visits 2 and 3)

Attach any non-standard instruments at the end of the application.

16.3 Conduct of study procedures or tests off-site by non-UCSF personnel:

Yes No

If yes, explain:

The primary site for the proposed study is the San Francisco Veterans Affairs Medical Center (SFVA), which will oversee all study procedures and will maintain all study data. The intervention itself will take place off-site at adult day programs that have active contracts with SFVA or other local VA facilities. Study sites will include: Marin Adult Day Health Center, Novato, CA; Institute on Aging, San Francisco, CA; Alzheimer's Services of the East Bay, Oakland, CA; and Catholic Charities, Santa Rosa, CA. Other study sites will be added to the protocol over time. Some study procedures may occur at other off-site locations at the request of caregivers (e.g., caregiver home). All research-related activities will be performed by research staff, who may be employees of UCSF, SFVA or NCIRE. This will include: screening potential study participants for eligibility; scheduling visits; obtaining informed consent/assent; performing baseline and follow-up assessment; delivering the intervention; documenting research activities; and entering and analyzing data. Staff at the study sites will NOT be engaged in research and will be responsible for referring potential participants to our research team for screening; escorting study participants to and from the exercise intervention space; assisting study participants who need to use the toilet; and providing space for our exercise instructors to deliver the intervention.

16.4 Sharing of experimental research test results with subjects or their care providers:

Yes No

If yes, explain:

Findings from the study may be shared with study participants or caregivers in aggregate form. Individual data will not be shared. Results may be shared by phone, letter or in person based on participant, caregiver or investigator preferences.

16.5 * Specimen collection for future research and/or specimen repository/bank administration:

Yes No

16.6 Time commitment (per visit and in total):

Participant with dementia

- consent: 1 hour

- baseline assessment: 1 hour
- intervention: 1 hour, 2-3 days/week, 4 months: 36-54 hours
- home visits: 1 hour, monthly, 4 months: 4 hours
- 4-month assessment: 1 hour
- 8-month assessment: 1 hour
- total: 44 to 62 hours over 10 months

Caregiver

- screening: 1 hour
- consent: 1 hour
- baseline assessment: 1 hour
- home visits: 1 hour, monthly, 4 months: 4 hours
- check-in calls: 15 minutes, monthly, 10 months: 2.5 hours total
- 4-month assessment: 1 hour
- 8-month assessment: 1 hour
- total: 11.5 hours over 10 months

16.7 Locations:

As described above, the primary site for this study is the San Francisco Veterans Affairs (SFVA), which will oversee all study procedures and will maintain all study data. The intervention itself will take place off-site at adult day programs that have active contracts with SFVA or other local VA facilities. In addition, some study procedures may occur at other off-site locations at the request of caregivers (e.g., caregiver home).

16.8 Describe the resources in place to conduct this study in a way that assures protection of the rights and welfare of participants:

The safety and welfare of study participants will be ensured by performing study procedures at adult day programs that study participants are already attending or are willing to attend or at locations chosen by caregivers (e.g., home). Study personnel who assess for eligibility, obtain consent and administer study questionnaires will be extensively trained in how to work with individuals with dementia and caregivers in a sensitive and respectful manner. Class size will be limited to 10 participants with 2 instructors to ensure the safety of study participants. Exercise instructors will be certified in at least one type of exercise training and will be extensively trained in how to safely work with individuals with dementia. Data will be maintained on secure VA or UCSF servers, VA-encrypted laptops, VA-approved thumb drives, VA-approved video recorders or in locked file cabinets. Subject identifiers will be used rather than personally identifying information on study forms whenever possible.

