17.0 Risks and Benefits

17.1 * Risks and discomforts:

Subjects will be assigned to a group by chance that will determine the order in which they receive the intervention and control programs. These programs may be less effective or have more side effects than other available programs. This will not be known until after the study is completed and the data have been analyzed. As with any program involving new exercises, participants with dementia may experience exercise-related injuries including muscle strain or soreness, joint pain or falls. The primary participant may find the video-recorded sessions of the study to be stressful or uncomfortable. In addition, participants with dementia or caregivers may find the baseline or follow-up assessments to be psychologically or emotionally distressing. Loss of privacy may occur if research data are viewed by individuals outside the research team. There also may be risks that are unforeseeable.

17.2 Steps taken to minimize risks to subjects:

Minimizing risk of exercise-related injury: The PLIÉ program was specifically designed to be safe for individuals with dementia. Class size is restricted to a maximum of 10 participants with 2 instructors, so that exercise instructors can carefully attend to each participant as needed. Movements are broken down into their component elements and slowly increase in difficulty and complexity over the course of the program. Step-by-step instruction is provided to minimize the cognitive demands of the program. Participants are never forced to do anything, and their individual choices and preferences are respected.

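### The only described route into the adverse event log is the monthly caregiver call; instructors, who see in-class injuries, have no stated recording step

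*Combined protocol and SAP*

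**What the plan says.** Section 16.1, under Adherence, Adverse Events and Co-Interventions, gives the collection method: "Adverse events will be assessed by calling caregivers on a monthly basis using a standardized questionnaire". When an event is reported, "caregivers will be asked if they occurred during or shortly after participating in PLIE or usual activities". The only class-level record named there serves another purpose: "Adherence will be monitored using class attendance logs".

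The Schedule of Evaluations in 16.1 agrees. Its text says that adverse events and co-interventions "will be assessed during monthly caregiver check-ins during the intervention period", and its table marks adverse events only in the column for monthly caregiver check-ins. Section 16.6 gives the length of the calls as "check-in calls: 15 minutes, monthly, 10 months: 2.5 hours total".

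On setting, 16.3 says "The intervention itself will take place off-site at adult day programs". For the monthly home visits, 16.1 says "Caregivers may participate in home visits"; nothing comparable is said about classes. On risk, 17.1 says that "participants with dementia may experience exercise-related injuries including muscle strain or soreness, joint pain or falls". Section 17.2 has instructors stop or modify an exercise when they see signs of pain, without a recording step.

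**The concern.** The harms the protocol expects from PLIÉ are exercise injuries, and many of these would happen in class. The person asked about them is a caregiver who has no stated role in the class. The participant, who might otherwise tell the caregiver, has memory loss or dementia. The person who saw the event is an instructor on the research team, and the plan does not say how that observation gets into the adverse event log.

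A serious fall would probably be passed on whatever the protocol says. A strain, joint pain that ends an exercise, or a fall without injury is easier to lose, and these are among the events most directly linked to the program. The Data Monitoring Committee reviews the log, so what is not entered is not reviewed. At stake is the completeness of safety monitoring and of any later description of harms.

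**Working it through.** **1. Does the plan leave room for caregivers at classes?** The inputs are the caregiver items in 16.6, in hours: screening 1, consent 1, baseline 1, home visits 4, calls 10 × 0.25 = 2.5, 4-month assessment 1, 8-month assessment 1.

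1 + 1 + 1 + 4 + 2.5 + 1 + 1 = 11.5 hours.

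This reproduces the stated total exactly, so 11.5 − 11.5 = 0 hours are budgeted for classes. The participant items also add up as stated: 1 + 1 + 36 + 4 + 1 + 1 = 44 and 1 + 1 + 54 + 4 + 1 + 1 = 62 hours. Class time is in the participant budget and absent from the caregiver budget.

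**2. Does any other section supply a route?**

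- Sections 18.1 and 19.1 of the Data and Safety Monitoring Plan (V1.1) cover reporting and committee review, but no further source of events.
- Section 17.2 mentions the centers' emergency procedures, and 16.1 mentions video-recording of some classes and optional home visits. None is described as adverse event collection.
- Sections 16.1 and 16.3 say that site staff are not engaged in research.
- Section 23.5 lets a participant continue after the caregiver withdraws. No substitute informant is named, so for that participant the one described route lapses.

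**3. How much class time does one call cover?** Section 16.6 gives 36 to 54 one-hour classes over 4 months. With one call a month, 36 / 4 = 9 and 54 / 4 = 13.5 classes per call.

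**4. How long would an event wait if the call were its only way into the log?** One month is 365.25 / 12 = 30.4 days, so the wait runs from 0 to about 30 days. If events are spread evenly over the interval (assumption), the mean is 30.4 / 2 = 15.2 days.

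**5. When are the calls made?** The overview in 16.1 places check-ins in the intervention period, and 11.1 uses a 4-month intervention period for the time when Group 1 is in PLIÉ and Group 2 has usual activities. Section 16.6 counts 10 months. With only 4 calls the caregiver total would be 9 + 4 × 0.25 = 10.0 hours; with 10 it is 9 + 10 × 0.25 = 11.5. Only the latter matches the stated total. The Usual Care text in 16.1 also has caregivers asked at check-ins about the past month's usual activities. The wider reading is the more likely one, but the two statements need to be brought into line.

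**The case against.** The strongest reply is that the plan omits a written step but forbids nothing. Under 16.3, running the intervention and documenting research activities are both research-staff work, so an instructor who sees an injury is already on the team. The study is described as minimal risk (23.7), classes are capped at 10 participants with 2 instructors (17.2), and an external committee reviews events. A single caregiver questionnaire used in both groups is also defensible in an unblinded waitlist trial, because events are then sought in the same way in each. All of this stands. It lowers the stakes and is a reason to keep the calls, but it does not supply the missing step.

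Several stronger inferences are tempting, and the documents do not support them:

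- *Events reach the team a month late.* Instructors are part of the team. Any delay is in entry to the log.
- *Expedited reporting must wait for a call.* Section 16.1 and the monitoring plan set a 5-working-day duty without tying it to a call. Setting the call interval against that limit would also mix minor soreness with serious events.
- *Caregivers decide relatedness.* They are asked about timing. Section 16.1 grades study-relatedness separately and does not give that task to the caregiver.
- *Usual-care months have no safety data.* The Usual Care text, the wording of the event question and the 10 months of calls all point the other way.
- *A safety endpoint is biased.* Sections 12.1 to 12.3 define no adverse event outcome or comparison.

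**Conclusion.** The point holds as a gap in how in-class events are captured. The monthly caregiver check-in is the only collection route described, caregivers have no stated role in classes, and the instructors who witness events have no stated way of logging them. Minor and moderate in-class events may be under-recorded, or logged only at the next call, with 9 to 13.5 classes between calls and a wait of up to about 30 days for events that depend on the call.

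The 15-day average rests on the assumption of even spacing. The number of events lost cannot be estimated, because the documents give neither an event rate nor the share that caregivers come to know about. If instructors report informally, the loss could be small. The consequence is for the completeness of monitoring and leaves the planned efficacy conclusions untouched. The change is worth making because it is cheap.

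**What to change.** - Add an event line to the class attendance log. At each session the instructor records any fall, injury, or pain that stops an exercise, and passes it the same day to whoever keeps the adverse event log.
- Keep the monthly caregiver calls in both groups through the 8-month visit, as the common source for any between-group comparison.
- Report instructor-logged events separately. They exist only while a participant is in PLIÉ, so setting them against usual care would make the program look more harmful simply because it was watched more closely.
- Reconcile the check-in period in the 16.1 overview with the 10 months of calls in 16.6, and say who answers the calls if a caregiver withdraws and the participant continues.

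The cost is one line on a log already kept for attendance, a short instruction to instructors, and an edit to 16.1 and 16.6. No extra staff are needed. The downside is the unequal detection just described, which separate reporting deals with.
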